## **6.3 Measures to Minimise Bias: Randomisation and Blinding**

### **6.3.1 The Process of Enrolment and Randomisation**

An IRT/RTSM will be used for the assignment of unique participant numbers and randomisation codes in the study. The participant numbers will be obtained during screening for all participants, after the signature of the ICF, while the randomisation codes will be assigned only to the participants proceeding to the maintenance phase of the study. Before the study is initiated, detailed instructions describing the process of IRT/RTSM usage, including the telephone number and call-in directions for the IRT and/or the log in information and directions for the RTSM, will be provided to each site in the IRT/RTSM user manual.

In case of rescreening, the rescreened participants should be assigned the same participant number as for the initial screening.

Study intervention will be dispensed at the study visits summarised in the SoA (Section 1.3) and can also be dispensed at unscheduled visits. Returned study intervention in unopened packets or sachets may be re-dispensed to the same participant. For study intervention that is sourced centrally, the IRT/RTSM will provide to the investigator(s) or pharmacists the kit identification number to be allocated to the participant at the dispensing visit. As the dosing regimen in the initiation phase is dependent on the participant's local S-K value obtained prior to the first SZC dose, this value will have to be provided to the system before any SZC is dispensed.

Direct-to-participant delivery of study intervention may be implemented where local regulations allow; instructions will be provided to the applicable investigator site(s) regarding dispensation of study intervention (ie, specific visits and delivery methods).

The study will aim at recruiting a certain minimum number of participants in the 2 cohorts described in inclusion criterion 5 (Section 5.1) as follows:

- (a) Cohort A: Hyperkalaemia ( $S\text{-}K > 5.0$  to  $\leq 6.5$  mmol/L) and on adequate or limited RAASI treatment due to hyperkalaemia; one half of all enrolled participants.
- (b) Cohort B: Normokalaemia ( $S\text{-}K \geq 3.5$  to  $\leq 5.0$  mmol/L) and on limited RAASI treatment due to high risk of hyperkalaemia; one third of all enrolled participants.

During the study, sites will be notified if the number of participants recruited in a particular cohort approaches a point where further recruitment in the cohort would hinder the achievement of the desired number of participants in the other cohort.

In this study, the randomisation will be stratified by 3 factors: country; inclusion criterion 5 (Section 5.1) categorisation as given above; and SGLT2 inhibitor and/or finerenone use at randomisation.

### 6.3.2 Break of the Blind

The randomisation code should not be broken except in medical emergencies when the appropriate management of the participant requires knowledge of the treatment randomisation. The IRT/RTSM will be programmed with blind-breaking instructions. In case of an emergency, in which the knowledge of the specific blinded study intervention (ie, SZC/placebo) will affect the immediate management of the participant's condition, the investigator has the sole responsibility for determining if unblinding of a participant's intervention assignment is warranted. Participant safety must always be the first consideration in making such a determination.

If a participant's intervention assignment is unblinded, the Sponsor must be notified within 24 hours after breaking the blind. The investigator should document and report the action to AstraZeneca, without revealing the treatment given to participant to the AstraZeneca staff.

AstraZeneca retains the right to break the randomisation code for SAEs that are unexpected and are suspected to be causally related to an investigational product and that potentially require expedited reporting to regulatory authorities. Randomisation codes will not be broken for the planned analyses of data until all decisions on the evaluability of the data from each individual participant have been made and documented.

### **6.3.3 Potentially Treatment-revealing Data**

The following information will be considered as potentially treatment revealing during the maintenance phase of the study:

- S-K (central laboratory)
- Serum bicarbonate (central laboratory)
- SZC/placebo dose
- Lisinopril/valsartan/irbesartan dose

To minimise the risk of revealing the treatment, the AstraZeneca study team will be blinded to the above.

The investigator site will be blinded to the central laboratory results/values of S-K and serum bicarbonate. However, if the S-K or serum bicarbonate laboratory results/values fall outside of the reference range with potential critical implications for the participant, the investigator and a pre-identified Sponsor contact will be notified.

Additional information about preserving the blind and maintaining study integrity will be detailed in another document. The clinical management of an individual participant is considered to have minimal risk of bias.

### **6.4 Study Intervention Compliance**

When participants are dosed at the site, they will receive study intervention directly from the investigator or designee, under medical supervision. The date of dose administration in the clinic will be recorded in the source documents.

When participants self-administer study intervention(s) at home, compliance with study intervention will be assessed at each visit. Compliance will be assessed primarily by counting returned sachets/tablets/capsules during the site visits and documented in the source documents.

A record of the number and strength of SZC/placebo sachets (5 or 10 g) and the number and strength of lisinopril/valsartan/irbesartan tablets/capsules dispensed to and returned by each participant must be maintained and reconciled with study intervention and compliance records. This information will be recorded in the source documents, together with the dates of the dispensation and return. In addition, the prescribed SZC/placebo and lisinopril/valsartan/irbesartan treatment, in terms of dosing and time of titration, will be recorded.

For the purpose of study reporting, compliance to SZC/placebo treatment regimen will then be evaluated by means of comparison between the number and type of sachets estimated to be taken by the participant, and the recorded prescription.

## 6.5 Concomitant Therapy

Any medication or vaccine (including over the counter or prescription medicines, vitamins, and/or herbal supplements) that the participant is receiving at the time of enrolment or receives during the study must be recorded along with:

- Reason for use
- Dates of administration including start and end dates
- Dosage information including dose and frequency

The Study Physician should be contacted if there are any questions regarding concomitant or prior therapy. Medication other than that described in the subsections below, which is considered necessary for the participant's safety and wellbeing, may be given at the discretion of the investigator.

### 6.5.1 Restricted Concomitant Medication

Restricted medications are listed in **Table 6**. Restricted medications taken outside the conditions as specified in the "Instruction" column, due to, eg, compelling medical reasons that necessitate such an action, will be considered as disallowed medications, the use of which constitutes a protocol deviation.

**Table 6** **Restricted Medications**

Type of medication/treatment	Instruction
Potassium binders including SPS, CPS, patiromer sorbitex calcium (Veltassa®)	Only permitted to be used as short-term rescue therapy to treat an AE of severe hyperkalaemia (recommended if S-K > 6.0 mmol/L)
ACEi/ARB other than the study ACEi/ARB	Not permitted concomitantly with any ACEi/ARB study drug after the initiation phase

ACEi, angiotensin converting enzyme inhibitor; AE, adverse event; ARB, angiotensin II receptor blocker; CPS, calcium polystyrene sulfonate; SPS, sodium polystyrene sulfonate; S-K, serum potassium.

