### **6.5.2      Rescue Medication**

Rescue therapy for controlling hyperkalaemia is defined as any short-term (24 to 48 hours) therapeutic intervention during the run-in and maintenance phases, that is considered necessary as per the investigator's judgment and in accordance with local practice patterns to reduce S-K in the setting of an AE of severe hyperkalaemia. Rescue therapy is recommended

in general if S-K > 6.0 mmol/L unless otherwise specified in the protocol (see Section 6.6.4). Rescue therapy may include, but is not limited to, insulin/glucose, beta adrenergic agonists, sodium bicarbonate as well as dialysis, or other forms of renal replacement treatments, and other potassium binders including SPS, CPS, patiromer sorbitex calcium (Veltassa®) given for short-term control of severe hyperkalaemia. SZC/placebo must be temporarily discontinued while rescue therapy is administered.

All potassium binders other than SZC are considered restricted medications and can be used only for short-term rescue. They must not be used for chronic treatment during the study. Any participant who receives chronic treatment with potassium binders other than SZC/placebo must be discontinued from SZC/placebo study intervention.

Rescue medication for hyperkalaemia will not be provided as part of study medications.

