##### **Visit 7 (2 days after Visit 6b/randomisation)**

- If S-K  $\geq 3.5$  and  $\leq 5.0$  mmol/L, continue lisinopril/valsartan at the same dose; the participant must return 5 ( $\pm 1$ ) days later to Visit 8 for a local S-K laboratory measurement.
- If S-K is  $> 5.0$  and  $\leq 5.5$  mmol/L and SZC/placebo IS NOT at maximum of 15 g QD, increase SZC/placebo to 15 g QD AND reduce lisinopril/valsartan one step. If lisinopril/valsartan is at the lowest dose, pause dosing and assess re-initiation of these agents at starting doses (STEP 1) during the next visit. The participant must return 5 ( $\pm 1$ ) days later to Visit 8 for a local S-K laboratory measurement.
- If S-K is  $> 5.0$  and  $\leq 5.5$  mmol/L and SZC/placebo IS at maximum of 15 g QD, reduce lisinopril/valsartan one step. If lisinopril/valsartan is at the lowest dose (STEP 1), pause dosing and assess re-initiation of these agents at STEP 1 starting doses during the next visit. The participant must return 5 ( $\pm 1$ ) days later to Visit 8 for a local S-K laboratory measurement.
- If S-K is  $> 5.5$  mmol/L and:
  - Lisinopril/valsartan is at the lowest dose, permanently discontinue lisinopril/valsartan and consider short-term rescue therapy and management of hyperkalaemia as per SoC at the investigator's discretion and local practice. Follow up at Visit 8 for monitoring of local S-K laboratory value.
  - Lisinopril/valsartan is at mid-range (STEP 2) or maximum dose (STEP 3), pause lisinopril/valsartan and SZC/placebo, and give short-term rescue therapy as per SoC at the investigator's discretion (24 to 48 hours rescue treatment); re-start SZC/placebo after rescue and increase to 15 g QD if not already at maximum. Follow up at Visit 8 for monitoring of local S-K laboratory value.

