### Unscheduled Visit (5 [ $\pm 1$ ] days after Visit 8)

- If S-K is  $\geq 3.5$  and  $\leq 5.0$  mmol/L and lisinopril/valsartan was paused at Visit 8, restart lisinopril/valsartan at starting dose and schedule follow-up visits as per KDIGO 2020 Clinical Practice Guideline for Diabetes Management in CKD ([KDIGO 2020](#), Practice Point 1.2.2); the participant will in addition follow the SoA (Section 1.3) and return for Visit 9.
- If S-K is  $> 5.0$  mmol/L, permanently discontinue lisinopril/valsartan if on treatment, and consider short-term rescue therapy and management of hyperkalaemia as per SoC at the investigator's discretion and local practice.

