#### **8.3.5 AEs Based on Examinations and Tests**

The results from the CSP-mandated laboratory tests and vital signs will be summarised in the CSR.

Deterioration as compared to baseline in protocol-mandated laboratory values and vital signs should therefore only be reported as AEs if they fulfil any of the SAE criteria, are the reason for discontinuation of treatment with the study intervention or are considered to be clinically relevant as judged by the investigator (which may include but is not limited to consideration as to whether treatment or non-planned visits were required or other action was taken with the study intervention, eg, dose adjustment or drug interruption).

If deterioration in a laboratory value/vital sign is associated with clinical signs and symptoms, the sign or symptom will be reported as an AE and the associated laboratory result/vital sign will be considered as additional information. Wherever possible the reporting investigator uses the clinical, rather than the laboratory term (eg, anaemia versus low haemoglobin value). In the absence of clinical signs or symptoms, clinically relevant deteriorations in non-mandated parameters should be reported as AE(s).

Hypokalaemia leading to a temporary or a permanent discontinuation of SZC or SZC/placebo should be reported as an AE.

Any new or aggravated clinically relevant abnormal medical finding at a physical examination as compared with the baseline assessment will be reported as an AE unless unequivocally related to the disease under study.

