### **Intensity Rating Scale:**

- Mild (awareness of sign or symptom, but easily tolerated)
- Moderate (discomfort sufficient to cause interference with normal activities)
- Severe (incapacitating, with inability to perform normal activities)

It is important to distinguish between serious and severe AEs. Severity is a measure of intensity whereas seriousness is defined by the criteria in Appendix G 2. An AE of severe intensity need not necessarily be considered serious. For example, nausea that persists for

several hours may be considered severe nausea, but not an SAE unless it meets the criteria shown in Appendix [G 2](#). On the other hand, a stroke that results in only a limited degree of disability may be considered a mild stroke but would be an SAE when it satisfies the criteria shown in Appendix [G 2](#).

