4.1.8 Concomitant Medications

4.1.8.1 Definitions and Derivations

Concomitant medications, including medications taken during the screening period, will be collected in the eCRF and classified by ATC classification and generic term.

Baseline medications for a particular phase are defined as medications with a start date no later than the beginning of the phase in question, and a stop date after the beginning of the phase (or ongoing at the end of study).

Concomitant medications for a particular phase are defined as medications which a patient takes during that phase. Explicitly, it is medications with a start date earlier than the end of the specific phase and a stop date during or after the same phase (or ongoing at the end of study). Missing start and stop dates will be handled as set out in Section 3.3.1.2.

A rescue medication is defined as a medication used in connection to the adverse event of severe hyperkalaemia requiring rescue as determined by the investigator.

Two types of medications are considered to be disallowed in the study:

- **A potassium binder is disallowed** if it is not a short term (≤ 2 days) rescue medication. Potassium binders are defined by the following ATC codes / ingredients:

Table 1: Disallowed potassium binders

| ATC code | Ingredients |
|----------|-------------------------------|
| V03AE | SODIUM POLYSTYRENE SULFONATE |
| V03AE | CALCIUM POLYSTYRENE SULFONATE |
| V03AE | PATIROMER |
| V03AE | PATIROMER CALCIUM |
| V03AE | PATIROMER SORBITEX CALCIUM |

- **RAASi medication is disallowed** if it is taken concomitantly with Valsartan or Lisinopril, after the initiation phase, as specified by the CSP.

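### Potassium-binder rescue given under Protocol 6.6.4 can be tabulated as disallowed medication and missed as rescue, because Table 6 and SAP 4.1.8.1 recognise rescue only through an AE of severe hyperkalaemia

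*Protocol*

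**What the plan says.** - Protocol 6.5.1, Table 6, on potassium binders: "Only permitted to be used as short-term rescue therapy to treat an AE of severe hyperkalaemia (recommended if S-K > 6.0 mmol/L". The text above the table makes use outside the stated condition a disallowed medication and a protocol deviation.
- Protocol 6.5.2 defines rescue as "any short-term (24 to 48 hours) therapeutic intervention during the run-in and maintenance phases", judged necessary by the investigator, in the setting of an AE of severe hyperkalaemia. It recommends rescue above 6.0 mmol/L in general, unless the protocol specifies otherwise, and points to 6.6.4.
- Protocol 6.6.4, Visit 7, S-K > 5.5 with lisinopril/valsartan at STEP 2 or 3: "pause lisinopril/valsartan and SZC/placebo, and give short-term rescue therapy as per SoC", at the investigator's discretion.
- Protocol 6.6.4, unscheduled visit after Visit 8: "If S-K is $> 5.0$ mmol/L, permanently discontinue lisinopril/valsartan if on treatment, and consider short-term rescue therapy".
- SAP 4.1.8.1: "A rescue medication is defined as a medication used in connection to the adverse event of severe hyperkalaemia requiring rescue as determined by the investigator". A binder is disallowed "if it is not a short term (≤ 2 days) rescue medication".
- SAP 4.1.8.2 summarises disallowed medications. SAP 3.3.5 lists excluded medication among the reasons for an important protocol deviation. SAP 4.5.1.2 tabulates participants with hyperkalaemia requiring rescue, and SAP 4.5.1.1 takes that category from the investigator's entry on the AE form.

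**The concern.** The instruction to treat and the rule for classifying the treatment rest on different things. Section 6.6.4 works from a potassium value. Table 6 and the SAP work from an AE that an investigator has labelled severe and in need of rescue. A site can follow 6.6.4 to the letter, use a binder, and have that use reported as a deviation and absent from the rescue table.

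The two errors are unlikely to fall evenly. Protocol Table 3 names hyperkalaemia as the risk for participants randomised to placebo, and 4.2.3 plans for rebound after withdrawal. At stake are the disallowed-medication, deviation and rescue summaries by arm, which describe how often placebo participants needed potassium-lowering treatment.

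**Working it through.** No sample size, power or event figure is involved, so the check sets the passages side by side.

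**Step 1. The rescue branches of Protocol 6.6.4.**

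| Visit | S-K (mmol/L) | Lisinopril/valsartan dose | Rescue | Action on study intervention | AE of severe hyperkalaemia required? |
|---|---|---|---|---|---|
| 7 | > 5.5 | Lowest | Consider | Lisinopril/valsartan stopped permanently | No |
| 7 | > 5.5 | STEP 2 or 3 | Give | Both interventions paused | No |
| 8, no rescue at Visit 7 | > 5.5 | STEP 1 | Consider | Lisinopril/valsartan stopped permanently | No |
| 8, no rescue at Visit 7 | > 5.5 | STEP 2 or 3 | Consider | Both interventions paused | No |
| Unscheduled | > 5.0 | Any | Consider | Lisinopril/valsartan stopped permanently if on treatment | No |

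Every branch can apply at 6.0 mmol/L or below: above 5.5 and up to 6.0 in the first four, above 5.0 and up to 6.0 in the last.

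**Step 2. Does 6.5.2 close the gap?** Its deferral to 6.6.4 is attached to the sentence recommending rescue above 6.0. The preceding sentence, which defines rescue, still requires an AE of severe hyperkalaemia. The deferral moves the S-K level and leaves the AE condition in place. Table 6 carries no deferral.

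**Step 3. Will there be an AE?** Usually. Under Protocol 8.3.5 deteriorations in mandated laboratory values "should therefore only be reported as AEs if they fulfil any of the SAE criteria", are the reason for stopping study intervention, or are judged clinically relevant. That judgment may take account of treatment given, unplanned visits, dose adjustment or drug interruption. Section 6 counts lisinopril/valsartan as study intervention, so permanent stopping meets the second ground. Pausing both interventions and giving rescue supports the third.

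**Step 4. Will the AE carry the flag?** That is not fixed. Protocol 8.3.2 collects whether the AE required rescue for severe hyperkalaemia as its own variable. The same section gives S-K bands for the intensity of hypokalaemia and none for hyperkalaemia. Two investigators treating the same value, for example 5.7, can answer differently.

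**Step 5. What the SAP does with the answer.** In logical form:
- rescue = medication linked to the flagged AE;
- disallowed binder = NOT (rescue AND ≤ 2 days);
- rescue table = participants with the flagged AE.

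If the flag is absent, the rescue condition is false. The binder is then disallowed whatever its duration, and the participant is not in the rescue table. If the flag is present and the course is within the day limit, both classifications are right. The outcome turns on the flag alone. Non-binder rescue (insulin/glucose, beta agonists, bicarbonate, dialysis) cannot become a disallowed binder, but without the flag it too is missed as rescue.

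**The case against.** The strongest reply is that the protocol already announces the exception: 6.5.2 sends the reader to 6.6.4, 6.6.4 sends the reader back, and the 6.0 level is only a recommendation. On the S-K level this stands. A reader might infer a flat contradiction between > 6.0 and > 5.5 or > 5.0, and the documents do not support that. Table 6 merely omits the cross-reference. It is also true that only one branch says to give rescue, and that one leaves discretion.

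A second reply is that an AE will nearly always exist. That stands as well (Step 3). What remains open is the label on the AE.

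A reader might go further and say that a participant without symptoms could never qualify, because Protocol Appendix G grades intensity as "Severe (incapacitating, with inability to perform normal activities". The documents do not make that link. Maximum intensity and the rescue flag are separate variables in 8.3.2, and SAP 4.5.1.1 takes the flag directly from the investigator.

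A reader might also argue that a 48-hour course starting part-way through a day spans three dates and so breaks the SAP's limit. The SAP gives no counting rule for binder duration. Its difference-plus-one convention is stated for event times and AE durations. Protocol 4.1.2 treats once-daily dosing for 48 hours as two days, with a third only if the result is late.

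Finally, hyperkalaemia AEs and S-K categories are tabulated separately (SAP 4.5.1.2 and 4.5.2), so the risk itself is not hidden. That stands, and it limits the harm to the rescue, disallowed-medication and deviation summaries.

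**Conclusion.** The point holds as a classification gap. Binder use that follows 6.6.4 is counted correctly only if the investigator flags the AE as severe hyperkalaemia requiring rescue, and the documents do not say when to do so. Misclassification is possible, not automatic.

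Its size is unknown. A reader might attach a participant count by assuming a rescue rate, but neither document gives a rate, the share of rescue given as binders, or how often the flag would be left unset. The SAP amendment history also reports premature termination, so the planned 1360 randomised is not a safe base. That placebo is affected more is an inference from the protocol's own account of rebound risk.

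A reader might infer an effect on the eGFR slope results. The main efficacy analyses exclude nothing for an important deviation (SAP 3.3.5). The supplementary slope analysis in SAP 4.2.1.3 censors at long-term potassium-lowering treatment, and no text equates that with failing the short-term rescue rule. SAP 3.3.5 mentions a possible analysis dropping data taken on disallowed medication, but it refers to a Section 4.2.7 that the current SAP does not contain, and none of the analyses listed in SAP 4.2 is of that kind.

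One assumption: the Appendix C flow chart was not legible in the text reviewed. Protocol 7.1.1 refers to severe hyperkalaemia as per that algorithm. If the chart sets an S-K level for severe, Step 4 is weaker for visits it governs, and the sponsor should say whether that level applies to the flag.

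**What to change.** **Protocol.** Reconcile Table 6, 6.5.2 and 6.6.4, so that it is clear how rescue under 6.6.4 stands in relation to the Table 6 condition and how sites are to flag it. Which S-K threshold or rescue duration is right is for the sponsor; this review takes no position.

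**SAP 4.1.8.1.** Classify short-term potassium-lowering treatment given under Protocol 6.5.2 or 6.6.4 as rescue if either source shows it: the investigator's AE flag, or the concomitant-medication record (reason for use and start and end dates). Use that follows 6.6.4 is then not counted as disallowed. Apply the same rule to the table of hyperkalaemia requiring rescue in SAP 4.5.1.2, so that the two outputs agree.

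**Cost.** Wording in both documents and a small programming change. Protocol 6.5 already collects reason for use and dates, so no new data are needed. As the study has ended early, the SAP and the study report are the practical places to act.
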